#### 2.4.3.3 NEDA

The proportion of subjects with no evidence of disease activity (NEDA) will be calculated at Week 96. A subject with NEDA is defined as a subject without evidence of disease activity, which is defined as a subject without relapses confirmed by the IRAP, without MRI activities (no T1 Gd+ lesions and no new/enlarging T2 lesions), and no 12-week Confirmed Disability Progression.

1. Any evidence of disease activity from Week 24 to Week 96 will be counted as not reaching NEDA. Any evidence of disease activity before Week 24 will not count.
2. In the case of early termination at any time point (including before Week 24), even if an event was not reported before early discontinuation, the subject will be considered as not reaching NEDA.

NEDA rates will be compared using logistic regression [REDACTED] with baseline adjustments the same as used in the primary endpoint analysis, without treatment duration offset, but including log-transformed baseline MRI counts (T1 unenhancing, T2, Gad enhancing).

To avoid zero values for the log transformation of MRI counts, 1 will be added to each observation before transforming.

#### 2.4.3.4 SDMT

The total score at one visit is defined as the total number of correct answers reported in the CRF. Impaired SDMT is defined as a decrease from baseline of at least four points at any post-baseline SDMT assessment up to the Week 96 visit. The proportion of impaired SDMT will be analyzed in all subjects within the modified intention to treat (mITT) population.

SDMT rates will be compared using logistic regression [REDACTED] with baseline adjustments the same as used in the primary endpoint analysis, without treatment duration offset, but including log-transformed baseline MRI counts (T1 unenhancing, T2, Gad enhancing). To avoid zero values for the log transformation of MRI counts, 1 will be added to each observation before transforming

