## 2.2.3 Modified Intention-to-Treat (mITT) Population

The modified Intention-to-Treat (mITT) population will consist of all subjects in the ITT population who received at least one dose of study medication and have at least one baseline and post baseline efficacy assessment. The primary efficacy analyses (of primary, secondary and tertiary efficacy endpoints, except MRI related) will be performed based on the mITT population.

The MRI related efficacy analyses will be performed on the subjects in mITT population who have baseline and post-baseline MRI efficacy assessments (mITT-MRI).

Subjects will be analyzed by randomized treatment group.

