## 2.4.2 Primary Efficacy Variable

### **Main statistical model and adjustment for covariates**

The primary analysis will be performed using the mITT with a Negative Binomial regression model to accommodate the potential over-dispersed data appropriately. The model will include the total number of confirmed relapses with onset between randomization date and the day of last treatment as response variable, treatment group, EDSS strata (baseline EDSS score  $\leq 3.5$  versus  $> 3.5$ ) and clinic region (defined in section 2.1.1) as covariates. There will be two treatment groups (teriflunomide or ublituximab). In order to account for different treatment durations among subjects, the log-transformed standardized treatment duration will be included in the model as an “offset” variable for appropriate computation of the annualized relapse rate. [REDACTED] will be used to assess the overall model with subjects in a repeated statement using a Generalized estimating equation (GEE) approach. The standardized treatment duration is defined as (date of last treatment – randomization date +1)/365.25.

Two-sided 95% confidence intervals of the rate ratio will be provided for the comparisons of ublituximab versus teriflunomide. The estimated relapse rate for each treatment group and the difference between them, together with the corresponding 2-sided 95% confidence intervals will be provided.

[REDACTED]

The “overall” estimated annualized relapse rates (number of relapses divided by the sum of years under treatment) will also be presented by treatment group.

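### The SDMT impairment model should adjust for baseline SDMT, and the plan should say how early leavers are classified

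*SAP*

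**What the plan says.** SAP 2.4.3.4 defines impairment as a "decrease from baseline of at least four points at any post-baseline SDMT assessment up to the Week 96 visit". The arms are compared by logistic regression "with baseline adjustments the same as used in the primary endpoint analysis, without treatment duration offset, but including log-transformed baseline MRI counts"; the counts are T1 unenhancing, T2 and Gd-enhancing. Protocol 8.9.2 describes the same model. The adjustments carried over come from SAP 2.4.2, where the primary model has treatment, EDSS stratum "and clinic region (defined in section 2.1.1) as covariates". Baseline SDMT appears in neither list.

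On who is analysed, SAP 2.4.3.4 says: "The proportion of impaired SDMT will be analyzed in all subjects within the modified intention to treat (mITT) population". To enter mITT (SAP 2.2.3) a subject must be dosed and "have at least one baseline and post baseline efficacy assessment"; that assessment need not be an SDMT. Protocol 8.9 allows imputation only in sensitivity analyses. SAP 2.5.1 leaves missing categorical data out of percentages unless something else is specified. For NEDA, the preceding endpoint, SAP 2.4.3.3 has an explicit rule: after early termination "the subject will be considered as not reaching NEDA". SDMT has no rule of either kind. Sensitivity analysis 5 (SAP 2.4.2), the dropout imputation for secondary outcomes, names Gd lesions, T2 lesions and 12-week CDP only.

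**The concern.** The outcome is a change from the subject's own baseline, cut at 4 points. A high baseline score is partly favourable measurement error, so a later fall of that size is more likely from a high start than from a low one. Baseline SDMT therefore predicts the outcome, and it is already collected. A model that spends three terms on MRI counts and omits it gives up power. SDMT is fifth in the fixed sequence and brain volume is sixth, so a miss at SDMT also ends confirmatory testing of brain volume.

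The second issue is ascertainment. The event is a fall seen at any assessment, and a subject followed for less time has fewer chances to show one. With no follow-up term, no imputation and no early-leaver rule, shorter follow-up can look like better cognition. Unequal dropout is conceivable here. Protocol 4.4.3 reminds subjects with a confirmed relapse that they may leave for an approved treatment, and asks for re-consent if they stay. The study is powered for 40% fewer relapses on ublituximab.

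**Working it through.** The documents give no event rate, effect size or power for SDMT impairment, so there is no planned figure to reproduce. The numbers below illustrate size on stated assumptions.

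**1. Own baseline as covariate, across the SAP**

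| Endpoint | SAP section | Own baseline in model |
|---|---|---|
| Gd and T2 lesion counts | 2.4.3.2 | yes |
| Brain volume change | 2.4.3.2 | yes |
| MSFC | 2.4.4.1 | yes |
| FIS | 2.4.4.3 | yes |
| MSQoL-54 | 2.4.4.4 | yes |
| Lesion volumes | 2.4.4.10 | yes |
| SDMT impairment | 2.4.3.4 | no |

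**2. What the covariate is worth**

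From the documents: 220 per arm (SAP 1.3), two-sided 0.05 (SAP 2.4), and a fall of at least 4 points at any of Weeks 24, 48 and 96 (protocol Tables 6 and 7). Assumed: SDMT standard deviation 12, test-retest correlation 0.7 to 0.9, practice gains of 1, 1.5 and 2 points at the three visits, and a treatment benefit of 2 points. In 2,000 simulated trials per setting, logistic models with treatment alone and with treatment plus baseline SDMT were fitted to the same data.

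| Correlation | Impaired, control / ublituximab | Power without | Power with | Gain (points) | SE of log odds ratio, without / with |
|---|---|---|---|---|---|
| 0.7 | 50.1% / 40.6% | 51.4% | 57.1% | 5.7 | 0.193 / 0.207 |
| 0.8 | 44.2% / 32.7% | 69.4% | 73.4% | 4.0 | 0.198 / 0.208 |
| 0.9 | 31.4% / 18.4% | 88.8% | 88.9% | 0.1 | 0.228 / 0.233 |

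Monte Carlo error on a power near 50% is √(0.5 × 0.5 / 2000) = 0.011. With no treatment effect, rejection without and with the covariate was 5.4% and 5.9%, 4.3% and 4.7%, and 4.1% and 4.1%. Monte Carlo error there is √(0.05 × 0.95 / 2000) = 0.005. EDSS, region and MRI counts were not simulated. If they carry part of the information in baseline SDMT, the gain is smaller.

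**3. What the literal early-leaver reading could do**

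Assumed: true impairment risk p = 30% in both arms; 45%, 70% and 100% of events apparent by Weeks 24, 48 and 96; a dropout proportion d spread evenly over the three intervals. The only dropout figure in the documents is an overall 10% allowance (SAP 1.3.1), with nothing by arm.

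- If nothing is seen after the last scheduled SDMT, the observed proportion is (1 − d)p + (d/3)(0 + 0.45p + 0.70p) = 0.30 − 0.185d.
- If the Early Withdrawal SDMT counts and catches half of that interval's new events, it is (1 − d)p + (d/3)(0.225p + 0.575p + 0.85p) = 0.30 − 0.135d.

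| Dropout | Early Withdrawal SDMT | Observed | Difference (points) | Odds ratio | Rejection under no effect |
|---|---|---|---|---|---|
| 10% v 10% | not used | 28.2% v 28.2% | 0 | 1.00 | 5.0% |
| 15% v 5% | not used | 27.2% v 29.1% | 1.9 | 1.10 | 7.2% |
| 15% v 5% | used | 28.0% v 29.3% | 1.4 | 1.07 | 6.1% |

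The second row in full: 0.30 − 0.185 × 0.15 = 0.27225 and 0.30 − 0.185 × 0.05 = 0.29075, a difference of 0.0185. The odds ratio is (0.29075/0.70925) / (0.27225/0.72775) = 1.096. Also z = 0.0185 / √(2 × 0.2815 × 0.7185 / 220) = 0.43, and rejection is 1 − Φ(1.96 − 0.43) + Φ(−1.96 − 0.43) = 7.2%. For true risks of 20% to 40%, the 15% v 5% gap gives 0.9 to 2.5 points across both cases.

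With a true 30% v 20% difference and no use of the Early Withdrawal SDMT, power is 68% with no dropout and 64% with 10% in each arm. It is 49% if the control arm has 15% dropout and ublituximab 5%, and 77% if these are reversed. Equal dropout creates no false difference, but it shrinks a real one slightly.

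**4. Subjects with no post-baseline SDMT**

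EDSS and MRI are scheduled at Week 12, but the first scheduled post-baseline SDMT is at Week 24 (protocol Tables 5 and 6). A subject can therefore be in mITT with no post-baseline SDMT. SAP 2.4.3.4 says to analyse every mITT subject; SAP 2.5.1 says to leave missing categories out. The exception clause in 2.5.1 does not settle which governs here.

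**The case against.** The strongest reply is that the plan is not biased as written. Randomization protects the comparison whether or not baseline SDMT is in the model. The power gain rests on assumed inputs and almost disappears at correlation 0.9. That stands: the covariate is an efficiency gain, not a correction. A reader might infer that the omission loses precision, but the standard error of the log odds ratio rises slightly when baseline is added. What improves is power, because the adjusted log odds ratio is larger relative to its standard error.

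A reader might also infer that the plan counts everyone who leaves early as unimpaired, or that someone leaving before Week 24 cannot be impaired. The documents support neither. No section states such a rule, and a leaver who has already fallen 4 points is impaired. SDMT is done at the Early Withdrawal from Treatment visit (protocol Table 7 and Appendix F), and the definition takes in a fall "at any post-baseline SDMT assessment up to the Week 96 visit". SAP 2.5.3 restricts efficacy data to scheduled visits, but its stated purpose is to keep out relapse fluctuations and it does not mention this visit. SAP 2.4.2 also allows follow-up after study drug is stopped, so stopping treatment need not end SDMT data. The different rule for NEDA is not in itself an error, since NEDA is a composite requiring absence of activity.

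The planned repeats help less than they seem to. An ITT analysis has the same missing rule. The per-protocol set requires at least 1.75 years of treatment, which selects after randomization.

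**Conclusion.** The missing covariate is a free improvement forgone: about 0 to 6 points of power with 220 per arm, on assumed variability, reliability, practice gains and effect, and with no bias from leaving it out. The early-leaver point is secondary and is a gap in specification. On the literal reading the artefact at 30% risk and 15% v 5% dropout is 1.4 to 1.9 percentage points, an odds ratio of at most about 1.10. It needs unequal dropout and vanishes without it. A reader might infer that it favours a particular arm. The documents give no dropout by arm, so neither its direction nor its actual size can be known from them. More dropout on teriflunomide would work against the sponsor's claim; more on ublituximab would work for it.

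**What to change.** In SAP 2.4.3.4 and protocol 8.9.2, add baseline SDMT total score as a continuous covariate. This loses no subjects, because the endpoint cannot be computed without a baseline score.

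In SAP 2.4.3.4, state that the Early Withdrawal SDMT counts as a post-baseline assessment. State how a subject with no post-baseline SDMT is classified, and align this with SAP 2.5.1. These sentences are needed in their own right, since a supportive table alone leaves the confirmatory test's handling of early leavers unchanged.

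Extend sensitivity analysis 5 to SDMT, or add a supportive analysis of time to first fall of at least 4 points, censored at the last SDMT. That censoring may itself be informative, so the analysis should stay supportive.

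The cost is one covariate, a few sentences and one supportive table, all from data already collected. The changes should be fixed before database lock and unblinding.

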#### 2.4.3.5 EDSS/Disability

12 week Confirmed Disability Progression (CDP) is defined as an increase in EDSS

- at least 1 point higher than the baseline EDSS if the baseline EDSS is  $\leq 5.5$
- at least 0.5 higher than the baseline EDSS if the baseline EDSS is  $> 5.5$

Disability progression is considered confirmed (CDP) when the increase in the EDSS is confirmed (same criteria) at a regularly scheduled visit 12 weeks after the initial documentation of neurological worsening (does not include unscheduled visits).

The time to onset of 12 week confirmed disability progression (CDP) will be the time to progression to the EDSS change defined above. For each of these events, the time from randomization to the date of the first measurement of the increased EDSS as required is the “time to event”. If no event occurs, the time to CDP is regarded as censored at the last scheduled EDSS assessment. Summary tables of progression to CDP will present the proportion of subjects who suffered CDP during the study at 2 years and associated 95% CIs for each treatment group. The median time-to-event with 2-sided 95% CIs as well as the proportion of subjects remaining event-free at times of interest will be estimated using Kaplan-Meier methods implemented with [REDACTED]. The proportion of subjects with 12-week confirmed disability progression will be summarized.

EDSS results will be summarized as continuous and categorical variables by scheduled assessment time point and treatment group. All data collected for assessment of EDSS will be listed.

#### 2.4.4 Tertiary Endpoints

All tertiary analyses will be assessed at a Type I error of 0.05 with no adjustment for multiplicity [REDACTED].

1. Change in MSFC score from baseline to Week 96
2. Time to Confirmed Disability Progression (CDP) for at least 24 weeks
3. Time to Confirmed Disability Improvement (CDI) for at least 12 weeks
4. Time to Confirmed Disability Improvement (CDI) for at least 24 weeks
5. Health outcomes (MSQoL-54 (inclusive of SF36); FIS, hospitalization, steroid use, time out of work)
6. Total volume of Gd enhancing T1 lesions per MRI scan over the treatment period
7. Volume of T2 lesions
8. Volume of hypointense T1 lesion component (black holes)
9. Proportion of subjects free of disability progression at 24 weeks, 48 weeks, and 96 weeks
10. Proportion of subjects with a relapse
11. Time to first confirmed relapse

##### 2.4.4.1 MSFC

Items collected per visit		
Timed 25-Foot Walk	Time for Trial 1 (sec)	TW1(visit)
	Time for Trial 2 (sec)	TW2(visit)
9-Hole Peg Test	Dominant Hand: Time for Trial 1 (sec)	PTD1(visit)
	Dominant Hand: Time for Trial 2 (sec)	PTD2(visit)
	Non-Dominant Hand: Time for Trial 1 (sec)	PTN1(visit)
	Non-Dominant Hand: Time for Trial 2 (sec)	PTN2(visit)
PASAT 3 seconds	PASAT 3" Total Score	PAS(visit)

Summarization steps
---------------------

Average 25-Foot Walk (summarizing the two trials of one assessment)	$TW(\text{visit}) = \text{Mean}(TW1(\text{visit}), TW2(\text{visit}))$	If one of the two (TW1, TW2) is missing at a visit, use the available value for TW If both are missing, use instructions in the next row.
Z-score leg	$Z_{\text{leg,average}}(\text{visit}) = - (TW(\text{visit}) - \text{mean}(TW(\text{baseline}, \text{all subjects in analysis population}))/SD(TW(\text{baseline}, \text{all subjects in the analysis population})))$	Note: The leftmost minus sign is intended to assign the same direction (higher=better) as for PASAT If subject's input TW(visit) is not available, the Z-score is set to -13.7.
Average 9-Hole Peg Test (summarizing the 4 trials – two of each hand)	$PT(\text{visit}) = \text{mean}(1/\text{mean}(PTD1(\text{visit}), PTD2(\text{visit})), 1/\text{mean}(PTN1(\text{visit}), PTN2(\text{visit})))$	Note: means are inverted to assign the same direction (higher=better) as for PASAT. If one of the two (PTx1, PTx2) is missing at a visit, use the available value. If both are missing for a hand, use 777 for this hand.
Z-score arm	$Z_{\text{arm,average}}(\text{visit}) = (PT(\text{visit}) - \text{mean}(PT(\text{baseline}, \text{all subjects in analysis population}))/SD(PT(\text{baseline}, \text{all subject in analysis population})))$	
Z-score cognitive	$Z_{\text{cognitive}} = (PAS(\text{visit}) - \text{mean}(PAS(\text{baseline}, \text{all subjects in analysis population}))/SD(PAS(\text{baseline}, \text{all subjects in analysis population})))$	
MSFC score	$MSFC(\text{visit}) = Z_{\text{leg,average}}(\text{visit}) + Z_{\text{arm,average}}(\text{visit}) + Z_{\text{cognitive}}$	

Change in MSFC will be tested using linear Mixed Models including all scheduled assessment time points with baseline as a covariate along with the other covariates as used in the primary analysis.

#### 2.4.4.2 Disability endpoints

24 week Confirmed Disability Progression (24 Week CDP) is defined as an increase of  $\geq 1.0$  point from the baseline EDSS score that is not attributable to another etiology (e.g., fever, concurrent illness, or concomitant medication – this information will be reflected in the assessments documented by the investigator. In the statistical analysis no further checks are necessary.) when the baseline score is 5.5 or less, and  $\geq 0.5$  when the baseline score is above 5.5. Disability progression is considered confirmed when the increase in the EDSS is confirmed at a regularly scheduled visit at least 24 weeks after the initial documentation of neurological worsening.

12 Week Confirmed Disability Improvement (12 Week CDI) is defined as a reduction from the baseline EDSS score of at least 1.0 point (or 0.5 points if the baseline EDSS score was  $>5.5$ ) that was sustained and confirmed at the next scheduled visit at least 12 weeks after the initial documentation of neurological improvement. Similarly, 24-week Confirmed Disability Improvement (24 Week CDI) requires an initial reduction from baseline EDSS score and a subsequent confirmation of the reduction at all regular scheduled visits for at least 24 Weeks after the initial documentation of neurological worsening.

The analysis of the time to 24-week CDP and CDI at 12 and 24 weeks will utilize the same approach as that used for 12-week CDP (including subject proportions).

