6.3.2 DISABILITY EVALUATION

Disability Progression

The method of disability progression calculation will be different than that of the relapsed confirmation. The EDSS score will be used to assess disability progression. EDSS assessment will be performed by the Examining Neurologist. The Examining Neurologist must not share the EDSS score with the Treating Neurologist. The EDSS assessment for disability progression will be performed at screening and on Week 1 Day 1 (prior to randomization) and Weeks 12, 24, 36, 48, 60, 72, 84 and 96. Disability progression is a post hoc analysis only and will not be calculated by the Evaluating Neurologist or other study staff.

The EDSS is based on a standard neurological examination, incorporating the following function systems (pyramidal, cerebellar, brainstem, sensory, bowel and bladder, visual, and cerebral) and ambulation rated and scores as function system scores (FS). Each FS score is an ordinal clinical rating scale ranging from 0 to 5 or 6. These ratings are then used in conjunction with observations and information concerning ambulation and used of assistive devices to determine the EDSS score. The EDSS is a disability scale that ranges in 0.5-point steps from 0 (normal) to 10 (death).

The randomization process must ensure that the baseline EDSS is assessed for the subject by the Examining Neurologist and is documented before treatment is assigned.

Disability progression can only be assessed from the EDSS scores performed at baseline and on Week 1 Day 1 and Weeks 12, 24, 36, 48, 60, 72, 84 and 96.

Disability progression is defined as an increase of ≥ 1.0 point from the baseline EDSS score that is not attributable to another etiology (e.g., fever, concurrent illness, or concomitant medication) when the baseline score is 5.5 or less, and ≥ 0.5 when the baseline score is above 5.5.

Disability progression is considered confirmed when the increase in the EDSS score is confirmed at regularly scheduled visits at least 12 or 24 weeks after the initial documentation of neurological worsening.

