8.9.2 SECONDARY EFFICACY VARIABLES

The key secondary outcomes will be tested using a hierarchical approach with the order specified below using a step-down procedure where each test is at a Type I error 0.05. If any endpoints fail to reach significance, then formal testing of significance of the subsequent secondary outcomes will not be performed.

1. Total number of gadolinium enhancing (Gd-enhancing) T1-lesions per MRI scan by Week 96.
2. Total number of new and enlarging T2 hyperintense lesions (NELs) per MRI scan by Week 96.
3. Time to Confirmed Disability Progression (CDP) for at least 12 weeks occurring during the 96-week, double-blind treatment period. *
4. Proportion of subjects with No Evidence of Disease Activity (NEDA) from Week 24 to Week 96.
5. Proportion of subjects reaching impaired SDMT (Symbol Digit Modalities Test) from baseline to Week 96.
6. Percentage change in Brain Volume from baseline to Week 96.

* Confirmed Disability Progression for at least 12 weeks during the 96-week treatment period will be analyzed using pooled data from the two identical studies TG1101-RMS301 and TG1101-RMS302.

The total number of gadolinium enhancing (Gd-enhancing) T1-lesions will be calculated as the sum of the individual number of lesions at weeks 12, 24, 48, and 96, divided by the total number of MRI scans of the brain. The total number of new and enlarging T2 hyperintense lesions will be calculated as the sum of the individual number of lesions at weeks 24, 48, and 96, divided by the total number of MRI scans of the brain. The MRI count variables will be assessed for differences between the treatment groups using negative binomial regression with an offset based on time on study and covariates, region, baseline EDSS strata, and baseline MRI counts. Percent brain volume change will be assessed between the two groups using linear mixed effects models [REDACTED] with covariates region, baseline EDSS strata, and baseline brain volume.

Disability progression is defined as an increase of ≥ 1.0 point from the baseline EDSS score that is not attributable to another etiology (e.g., fever, concurrent illness, or concomitant medication) when the baseline score is 5.5 or less, and ≥ 0.5 when the baseline score is above 5.5. Disability progression is considered confirmed when the increase in the EDSS score is confirmed at regularly scheduled visits at least 12 or 24 weeks after the initial documentation of neurological worsening.

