Time Required: | Full day; *Approximately 3 – 5 hours plus time for MRI*

Treatment: | Initiate the teriflunomide rapid elimination process (11 days) via activated charcoal or cholestyramine

Tests: | Serum Pregnancy Test; *must be negative results*
 MRI
 12 lead ECG

Clinical Assessments: | Adverse Event
 Concomitant medications
 EDSS, MSFC, MSQOL54, SDMT, FIS and neurological examination
 Physical examination/vital signs

Labs: | Hematologic profile; *CBC/FBC with differential and platelet count*
 Serum chemistry panel;

Labs:
 (see Laboratory Manual for full details, instructions, and shipping information)

Serum Chemistry		
Albumin	Glucose	SGPT [ALT]
Alkaline phosphatase	LDH	Sodium
Bicarbonate	Magnesium	Total bilirubin
BUN	Phosphorus	Total Protein
Calcium	Potassium	Uric acid
Chloride	SGGT	Indirect/direct bilirubin
Creatinine	SGOT [AST]	

Pancreatic Enzyme
 Absolute B cell lymphocyte count and % B cell
 Urinalysis
 Fibrinogen
 Teriflunomide Drug Concentration Test
 Quantitative Immunoglobulin

Documents / Forms: | Informed Consent Form
 eCRF documentation
 AE and SAE Reporting (If applicable)
 Sample shipping
 Subject diary review and teriflunomide or oral placebo accountability

Drug Preparation / Dispensation: | None

**Timing and
Sequence
Considerations:**

Once signed consent is obtained, procedures can be scheduled for the day at Investigator and subject convenience.

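### 24-week confirmed disability progression, as the SAP defines it, ignores the visit between onset and confirmation, so it is not nested in 12-week progression

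*SAP*

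**What the plan says.** **24-week CDP (tertiary).** SAP 2.4.4.2 asks for an EDSS rise over baseline of at least 1.0 point, or 0.5 if baseline is above 5.5, that is "confirmed at a regularly scheduled visit at least 24 weeks after the initial documentation of neurological worsening". One later visit is enough.

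**Improvement, same section.** 12-week CDI must be "sustained and confirmed at the next scheduled visit at least 12 weeks after the initial documentation of neurological improvement". 24-week CDI needs "subsequent confirmation of the reduction at all regular scheduled visits for at least 24 Weeks". Protocol 8.9.4 has the same two rules.

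**12-week CDP (key secondary 3).** SAP 2.4.3.5 confirms it "at a regularly scheduled visit 12 weeks after the initial documentation of neurological worsening" and excludes unscheduled visits. Protocol 8.9.2 covers both durations in one sentence: "confirmed at regularly scheduled visits at least 12 or 24 weeks after the initial documentation of neurological worsening". The synopsis and Protocol 4.4.4 and 6.3.2 say essentially the same. 12-week CDP also enters key secondary 4, because NEDA requires "no 12-week Confirmed Disability Progression" (SAP 2.4.3.3).

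**Visits.** Scheduled post-baseline EDSS is at Weeks 12, 24, 36, 48, 60, 72, 84 and 96 (Protocol 4.4.4). Protocol 5.2 lets a scheduled non-infusion visit be skipped and recorded as not done when a suspected relapse occurs there. SAP 2.5.3 uses only scheduled-visit efficacy measurements.

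**The concern.** With 12-weekly visits, exactly one scheduled EDSS lies between onset and the visit 24 weeks later. The SAP makes that visit count for improvement but not for progression. Two separate temporary rises with a normal score between them can then be counted as one confirmed progression, dated to the first rise. A longer confirmation period should give a stricter endpoint, and every 24-week event should also be a 12-week event. As written, a results table could show subjects with 24-week but no 12-week CDP.

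The 12-week wording matters for a different reason. It defines a key secondary endpoint that gates key secondaries 4 to 6 (SAP 2.4.3.1) and is a NEDA component. If the two documents can be programmed differently, event status or onset date may depend on which one is followed.

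**Working it through.** The documents give no CDP event rate, so there is no stated figure to reproduce. The check applies each rule literally to every possible sequence of up (threshold met) and down over the 8 scheduled visits: 2^8 = 256 complete sequences.

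| Rule | Condition over 8 visits | Count |
|---|---|---|
| SAP 12-week CDP | two adjacent visits up | 256 − 55 = 201 |
| Protocol 12-week, any later visit | any two visits up | 256 − 1 − 8 = 247 |
| Protocol 12-week, next scheduled visit | two adjacent visits up | 201 |
| SAP 24-week CDP as written | two visits up, at least two positions apart | 256 − 1 − 8 − 7 = 240 |
| Sustained 24-week CDP | three consecutive visits up | 256 − 149 = 107 |

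Here 55 is the number of sequences with no two adjacent ups and 149 the number with no three in a row. The 1, 8 and 7 are the sequences with no up, one up, and a single adjacent pair.

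**Nesting.** Sequences that are 24-week but not SAP 12-week events have no adjacent ups and at least two ups: 55 − 1 − 8 = 46. In 74 more, both events occur but the 24-week onset is earlier. If only the first visit at least 24 weeks after onset may confirm, the number of 24-week events falls from 240 to 192. The example at Weeks 12, 24 and 36 is still an event. Non-nested sequences are then 55 − 28 = 27, where 28 is the number with all ups at least three positions apart.

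**Against a sustained rule.** 240 − 107 = 133 sequences are events only because the intervening visit is ignored. Another 44 keep an event with a different onset.

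**12-week wording.** The literal any-later-visit reading adds 247 − 201 = 46 events and moves onset earlier in 74. The next-scheduled-visit reading matches the SAP on all 256. The rules then part only when the +12-week visit is missing. Up at Week 12, missing at Week 24, up at Week 36 and down afterwards is an event if the next available visit may confirm, and not under the SAP.

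**Illustrative size (assumed rates).** Take temporary rises at 1%, 3% or 5% of visits in subjects without true progression. The columns below are the chance that the next visit is also up; the first treats visits as independent, so its persistence equals the rise rate.

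| | Independent | 15% | 25% | 50% |
|---|---|---|---|---|
| 24-week as written, % | 0.20 / 1.7 / 4.4 | 0.27 / 1.6 / 4.1 | 0.41 / 1.9 / 4.1 | 0.92 / 3.0 / 5.4 |
| SAP 12-week, % | 0.07 / 0.6 / 1.7 | 0.91 / 2.7 / 4.5 | 1.4 / 4.1 / 6.8 | 2.0 / 5.9 / 9.8 |
| 24-week without 12-week, % | 0.2 / 1.6 / 4.1 | 0.12 / 1.0 / 2.8 | 0.08 / 0.7 / 1.9 | 0.02 / 0.19 / 0.51 |

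A second set of assumptions lets new worsening start at 3% to 5% of visits and persist with probability 0.5 to 0.85 (simulated, complete data). 24-week CDP is then 5.4, 9.1, 12.6 and 15.1% as written against 4.4, 8.5, 12.3 and 13.5% sustained: gaps of 1.0, 0.6, 0.3 and 1.6 points. With 5% of visits missing, the next-available 12-week reading exceeds the SAP rule by 0.1 to 0.2 points.

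**The case against.** The endpoint is named as progression for at least 24 weeks, and the text asks that the increase itself be confirmed. A score that falls back and later rises again is not naturally the same increase. This is a fair guide to intent. It does not settle the derivation, because the same section spells out the sustained condition for improvement and leaves it out for progression.

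The stronger objections concern weight, and they stand. 24-week CDP is tertiary, has no multiplicity adjustment and gates nothing. A reader might infer from 240 against 201 that 24-week CDP will be the more frequent endpoint. Those are unweighted patterns, and with 15% or more persistence the order reverses at all three assumed rates.

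A reader might also infer that the protocol and SAP define two different key secondary endpoints. With complete data that needs the reading in which any two raised visits, however far apart, make an event. Under the next-scheduled-visit reading they agree throughout. Protocol 8 also leaves full detail to the SAP, whose 12-week rule can be programmed as it stands. What remains is the missing +12-week visit, which Protocol 5.2 makes possible at non-infusion EDSS visits such as Weeks 12, 36, 60 and 84.

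Finally, EDSS is collected at the Early Withdrawal visit ("EDSS, MSFC, MSQOL54, SDMT, FIS and neurological examination", Protocol Appendix F), which might suggest an open question about confirmation there. It is largely closed: Protocol 6.3.2 says "Disability progression can only be assessed from the EDSS scores performed at baseline and on Week 1 Day 1" and the listed weeks, and SAP 2.4.3.5 and 2.5.3 admit scheduled visits only.

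**Conclusion.** The point holds for 24-week CDP. As written, the rule accepts up/down/up, differs from the improvement rule beside it, and is not nested in 12-week CDP (46 of 256 complete sequences). The counts establish that the rules differ logically; they do not estimate how many subjects are affected. The size is unknown because the documents give no EDSS fluctuation rate. Under the assumptions tried, 24-week CDP without 12-week CDP ranges from 0.02% to 4.1% of subjects without true progression, and is smallest when rises persist.

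Nothing here shows a bias in the treatment comparison or a threat to the confirmatory tests; the direction of any effect is not established. For 12-week CDP the finding is a wording mismatch with a small effect if the protocol means the next scheduled visit. It is worth closing because that endpoint is confirmatory and feeds NEDA.

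**What to change.** 1. **24-week CDP.** In SAP 2.4.4.2 and the matching protocol text (synopsis, 4.4.4, 6.3.2, 8.9.2), require the EDSS threshold at onset and at every scheduled visit through the one at +24 weeks, as for 24-week CDI. With complete data this gives the 107 sustained sequences, all of which are 12-week events.
2. **12-week CDP.** Align the protocol to the SAP: threshold met at onset and at the scheduled visit 12 nominal weeks later. The SAP definition of key secondary 3 is then unchanged, including with missing visits.
3. **Missing visits.** Show a rule that bridges one missing scheduled visit as a sensitivity analysis only. Over the 3^8 = 6561 up/down/missing sequences it would add 544 12-week events to the SAP's 3217 and move onset earlier in 331 others, so it should not enter the main definition of a confirmatory endpoint.

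The cost is wording in two documents and CDP programming, with no new data. There will be fewer 24-week events: under independent rises, about 0.2%, 1.7% or 4.4% of subjects without true progression stop counting. 24-week events that span a missing visit will appear only in the sensitivity analysis (1037 sequences under the strict rule against 2116 when one missing visit is bridged).
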